## 2.6 Interim Analysis

No interim analysis is planned.

## 2.7 Determination of Sample Size

There are no available clinical data for Restylane Volyme studied under conditions similar to the current study. However, based on what is seen in clinical studies of injectable fillers in the facial areas, it is reasonable to assume a response rate of at least 70% in the Restylane Volyme treatment group at Month 6. For the no treatment control group, response rates as high as 35% have been observed in Glogau et al. Based on this, it was assumed that the response rate will be maximum 35% in the no-treatment control group at Month 6.

CCI

## 2.8 Changes in the Analysis Planned in the Protocol

 GALDERMA	<small>Title</small> SAP, 43CH1626, Restylane Volyme Midface	<small>Doc id</small> MA-35135
---	--	--

## 4 Appendix A1: Study Subjects

### 4.1 Analysis Populations

**Table 4-1: Analysis populations**

Site	Group	Subject number	Safety		FAS		PP	
			n	%	n	%	n	%
Site 1	A	1xx-1xx						
	B	1xx-1xx						
Site 2	A	2xx-2xx						
	B	2xx-2xx						
Site 3	A	3xx-3xx						
	B	3xx-3xx						
Site 4	A	4xx-4xx						
	B	4xx-4xx						
Site 5	A	5xx-5xx						
	B	5xx-5xx						
Total (N)								

% = n/N\*100

### 4.2 Protocol Deviations

**Table 4-2: Protocol deviations excluding subjects from PP population, Group B**

Protocol deviation	Number of subjects 	Subject numbers
Total		

1) The same subject may have been excluded from PP for more than one reason.

 GALDERMA	Title SAP, 43CH1626, Restylane Volyme Midface	Doc id MA-35135
--	---	---------------------------

**Table 4-3: Protocol deviations not excluding subjects from PP population, Group A and B**

Protocol deviation	Group A		Group B		Total
	Number of subjects 	Subject numbers	Number of subjects 	Subject numbers	
Total					

1) A single subject may have reported several protocol deviations.

2017-11-03 11:43

Effective date:

Effective

Version: 1.0

 GALDERMA	Title SAP, 43CH1626, Restylane Volyme Midface	Doc id MA-35135
---	---	---------------------------

### 4.3 Subject disposition

**Table 4-4: Disposition of all subjects**

Site	Group	Screened subjects		Enrolled subjects		Subject numbers	Treated subjects		Completed subjects		Withdrawn subjects	
		n	%	n	%		n	%	n	%	n	%
Site 1	A					1xx-1xx						
	B					1xx-1xx						
Site 2	A					2xx-2xx						
	B					2xx-2xx						
Site 3	A					3xx-3xx						
	B					3xx-3xx						
Site 4	A					4xx-4xx						
	B					4xx-4xx						
Site 5	A					5xx-5xx						
	B					5xx-5xx						
Total (N)												

% = n/N\*100

**Table 4-5: Subject accountability by visit: subjects randomized to treatment with Restylane Volyme, Group B**

Visit	Number of subjects			
	Completed	Missed	Withdrawals	Continuing in study
Baseline/initial treatment				
4W follow-up/optional touch-up				
4W follow-up after last treatment				
3M after last treatment				
6M after last treatment				
9M after last treatment				
12M after last treatment				

[figure not shown]
 GALDERMA	Title SAP, 43CH1626, Restylane Volyme Midface	Doc id MA-35135
---	---	---------------------------

**Table 4-6: Subject accountability by visit: subjects randomized to no-treatment control, group B**

Visit	Number of subjects			
	Completed	Missed	Withdrawals	Continuing in study
Baseline				
4W follow-up				
3M follow-up				
6M follow-up/treatment				
4W follow-up/optional touch-up				
4W follow-up after last treatment				
3M after last treatment				
6M after last treatment				

2017-11-03 11:43

Effective date:

**Figure 4-1: Subject accountability by visit in Group A****Effective**

[figure not shown]
Version: 1.0

2017-11-03 11:43

Effective date:

**Effective**

Version: 1.0

**Figure 4-2: Subject accountability by visit in Group B**

	Title SAP, 43CH1626, Restylane Volyme Midface	Doc id MA-35135
--	---	---------------------------

**Table 4-7: Withdrawn subjects, Group A**

Site	Subject number	Date of treatment		Last visit performed	Date of withdrawal	Reason for withdrawal
		Initial treatment	Optional touch-up treatment			

**Table 4-8: Withdrawn subjects, Group B**

Treatment group	Site	Subject number	Date of treatment		Last visit performed	Date of withdrawal	Reason for withdrawal
			Initial treatment	Optional touch-up treatment			
Restylane Volyme							
Control							

 GALDERMA	<small>Title</small> SAP, 43CH1626, Restylane Volyme Midface	<small>Doc id</small> MA-35135
--	--	--

**Table 4-9: Screening failures**

Reason for screening failure	Group A		Group B		Total
	Screening number	Number of subjects	Screening number	Number of subjects	

## 5 Appendix A2: Demographics

### 5.1 Demographics and baseline characteristics

**Table 5-1: Summary of demographics and baseline characteristics, Safety population**

Characteristics	Parameter	Group A N = xx	Group B		
			Restylane Volyme N = xxx	Control N = xx	Total N = xxx
Age (years)	N				
	Mean				
	SD				
	Median				
	Minimum				
	Maximum				
Gender					
Female	n (%)				
Male	n (%)				
Ethnic origin					
Han Chinese	n (%)				
Other 	n (%)				
Baseline BMI	N				
	Mean				
	SD				
	Median				
	Minimum				
	Maximum				
Baseline MMVS score, Blinded Evaluator					
right side					
Score 2	n (%)				
Score 3	n (%)				
Score 4	n (%)				

% = n/N\*100

1) Specification of Other: ..., ..., .....

2017-11-03 11:43

Effective date:

*Effective*

Version: 1.0

 GALDERMA	Title SAP, 43CH1626, Restylane Volyme Midface	Doc id MA-35135
---	---	---------------------------

Characteristics	Parameter	Group A N = xx	Group B		
			Restylane Volyme N = xxx	Control N = xx	Total N = xxx
left side					
Score 2	n (%)				
Score 3	n (%)				
Score 4	n (%)				
CCI					

% = n/N\*100

 GALDERMA	Title SAP, 43CH1626, Restylane Volyme Midface	Doc id MA-35135
--	---	---------------------------

## 5.2 Medical history

**Table 5-2: Subjects reporting medical history/concurrent diseases and number of conditions by MedDRA System Organ Class (SOC) in Group A, Safety population**

Primary SOC	Total			Ongoing at study start		
	Subjects		Conditions	Subjects		Conditions
	n	%	n	n	%	n
Total (N)						

% = n/N\*100

1) A single subject may have reported medical history/concurrent diseases by more than one primary SOC category.

 GALDERMA	Title SAP, 43CH1626, Restylane Volyme Midface	Doc id MA-35135
---	---	---------------------------

**Table 5-3: Subjects reporting medical history/concurrent diseases and number of conditions by MedDRA System Organ Class (SOC) in Group B, Safety population**

Primary SOC	Restylane Volyme N = xxx						Control N = xx					
	Total		Ongoing at study start		Total		Ongoing at study start					
	Subjects	Conditions	Subjects	Conditions	Subjects	Conditions	Subjects	Conditions	Subjects	Conditions	Subjects	Conditions
	n	%	n	n	%	n	n	%	n	n	n	n
Total (N)												

 % = n/N\*100

1) A single subject may have reported medical history/concurrent diseases by more than one primary SOC category.

2017-11-03 11:43

Effective date:

**Effective**

Version: 1.0

**Table 5-4: Prior use of facial fillers or implants, Safety population**

Fillers/implants	Group A N = xx		Group B					
			Restylane Volyme N = xxx			Control N = xx		
	Subjects		Filers/implants	Subjects		Fillers/implants	Subjects	
	n	%	n	n	%	n	n	%
Hyaluronic Acid (HA)								
Permanent implant								
Semi-permanent implant								
Collagen								
Other 								
Total								

 $\% = n/N*100$ 

1) Specification of Other: ...., ...., .....

2) A single subject may have had several fillers of implants.

**Table 5-5: Prior use of other facial dermatological procedures, Safety population**

Procedure	Group A N = xx		Group B					
			Restylane Volyme N = xxx			Control N = xx		
	Subjects		Procedures	Subjects		Procedures	Subjects	
	n	%	n	n	%	n	n	%
Botulinum toxin injection								
Resurfacing								
Mesotherapy								
Face-lift								
Autologous Fat transplantation								
Other 								
Total								

 $\% = n/N*100$ 

1) Specification of Other: ...., ...., .....

2) A single subject may have had several facial dermatological procedures.

 GALDERMA	Title SAP, 43CH1626, Restylane Volyme Midface	Doc id MA-35135
---	---	---------------------------

## 6 Appendix A3: Concomitant medication and procedures

### 6.1 Concomitant medication

**Table 6-1: Subjects reporting concomitant medication, Safety population**

Concomitant medication	Any concomitant medication											
	Group A N = xx				Group B							
					Restylane Volyme N = xxx				Control N = xx			
	No		Yes		No		Yes		No		Yes	
	n	%	n	%	n	%	n	%	n	%	n	%
Ongoing at study start												
Initiated during study												
Total 												

% = n/N\*100

1) A single subject might have had concomitant medication ongoing at study start and initiated during study.

**Table 6-2: Subjects reporting concomitant medication and number of medications by reason, Safety population**

Reason for concomitant medication	Group A N = xx				Group B							
					Restylane Volyme N = xxx				Control N = xx			
	Subjects		Number of medications		Subjects		Number of medications		Subjects		Number of medications	
	n	%	Total	Ongoing at study end	n	%	Total	Ongoing at study end	n	%	Total	Ongoing at study end
Related Adverse Event												
Unrelated Adverse Event												
Medical History												
Other												
Total 												

% = n/N\*100

1) A single subject may have reported concomitant medication for several reasons.

2017-11-03 11:43

Effective date:

Effective

Version: 1.0

**Table 6-3: Subjects reporting concomitant medication and number of medications by ATC code, Safety population**

ATC code	ATC text	Group A N = xx		Group B			
				Restylane Volyme N = xxx		Control N = xx	
		Subjects	Medications	Subjects	Medications	Subjects	Medications
		n	%	n	n	n	n
Total							

 $\% = n/N*100$ 

1) A single subject may have reported several types of concomitant medication.

**Table 6-4: Subjects reporting concomitant medication taken due to an AE by ATC cod in Group A, Safety population**

ATC code	ATC text	Concomitant medication		Adverse Event	
		Subjects	Medications	PT	Related AE
		n	n		
					Yes/No
Total					

 $\% = n/N*100$ 

1) A single subject may have reported several types of concomitant medication.

Note: if too much data for unrelated AEs then update this and the next table for related AEs only.

**Table 6-5: Subjects reporting concomitant medication taken due to an AE by ATC code in Group B, Safety population**

ATC code	ATC text	Concomitant medication		Adverse Event	
		Subjects	Medications	PT	Related AE
		n	n		
					Yes/No
Total					

 $\% = n/N*100$ 

1) A single subject may have reported several types of concomitant medication.

## 6.2 Concomitant procedures

**Table 6-6: Subjects reporting concomitant procedures and number of procedures by reason, Safety population**

Reason for concomitant procedure	Group A N = xx		Group B					
			Restylane Volyme N = xxx		Control N = xx			
	Subjects		Procedures		Subjects		Procedures	
	n	%	n	n	%	n	%	n
Adverse Event								
Medical History								
Other								
Total								

% = n/N\*100

1) A single subject may have reported procedures for several reasons.

Please consider to add a table regarding “Concomitant procedures due to a related AE”.

**Table 6-7: Subjects reporting concomitant procedures and number of procedures, Safety population**

Concomitant procedure	Group A N = xx		Group B					
			Restylane Volyme N = xxx		Control N = xx			
	Subjects		Procedures		Subjects		Procedures	
	n	%	n	n	%	n	%	n
Total								

% = n/N\*100

1) A single subject may have reported several concomitant procedures.

Note: if too much data for unrelated AEs then update this table for related AEs only.

## 7 Appendix A4: Treatment procedure

**Table 7-1: Exposure to study treatment, Safety population**

Assessment (right and left midface combined)	Parameter	Group A N = xx	Group B	
			Restylane Volyme N = xxx	Control N = xx
Volume injected (mL) at initial treatment	N			
	Mean (SD)			
	Median			
	Minimum, Maximum			
Volume injected (mL) at touch-up	N			
	Mean (SD)			
	Median			
	Minimum, Maximum			
Total volume injected (mL) at initial treatment and touch-up	N			
	Mean (SD)			
	Median			
	Minimum, Maximum			
Depth of injection at initial treatment				
Subcutaneous	n (%)			
Supraperiosteal	n (%)			
Other 	n (%)			
Depth of injection at touch-up				
Subcutaneous	n (%)			
Supraperiosteal	n (%)			
Other 	n (%)			
Injection method at initial treatment				
Linear retrograde	n (%)			
Small aliquots	n (%)			
Fanning injection technique	n (%)			
Other 	n (%)			

Effective date: 2017-11-03 11:43

Effective date:

*Effective*

Version: 1.0

Assessment (right and left midface combined)	Parameter	Group A N = xx	Group B	
			Restylane Volyme N = xxx	Control N = xx
Injection method at touch-up				
Linear retrograde	n (%)			
Small aliquots	n (%)			
Fanning injection technique	n (%)			
Other 	n (%)			

% = n/N\*100

- 1) Specification of Other: ...., ...., ....
- 2) Specification of Other: ...., ...., ....
- 3) Specification of Other: ...., ...., ....
- 4) Specification of Other: ...., ...., ....

**Table 7-2: Treatment procedure, Safety population**

Time Point	Assessment (right and left midface combined)	Category	Group A N = xx	Group B	
				Restylane Volyme N = xxx n (%)	Control N = xx n (%)
Initial treatment	Local anaesthesia used?	No			
		Yes			
		Whereof topical cream			
		Whereof local infiltration			
Touch-up	Local anaesthesia used?	No			
		Yes			
		Whereof topical cream			
		Whereof local infiltration			
Initial treatment	Post-treatment care	None			
		Massage			
		Ice pack			
		Other 			
Touch-up	Post-treatment care	None			
		Massage			
		Ice pack			
		Other 			

% = n/N\*100

1) Specification of Other: ...., ...., ....

2) Specification of Other: ...., ...., ....

Any device deficiencies will be listed in text or in a separate table, as appropriate.

2017-11-03 11:43

Effective date:

*Effective*

Version: 1.0

	<small>Title</small> SAP, 43CH1626, Restylane Volyme Midface	<small>Doc id</small> MA-35135
--	--	--

## 8 Appendix A5: Post-treatment examinations

**Table 8-1: Subjects with change from baseline in post-treatment BMI  $\geq 2$  units, Safety population**

Group A		Group B	
Number of subjects	Subject numbers	Number of subjects	Subject numbers

 GALDERMA	Title SAP, 43CH1626, Restylane Volyme Midface	Doc id MA-35135
---	---	---------------------------

## 9 Appendix A6: Effectiveness Evaluation for Group B

### 9.1 Primary analysis

#### 9.1.1 MMVS responder rate at Month 6

**Table 9-1: MMVS responder rate at Month 6 by treatment, Blinded Evaluator**

Population	Assessment/Time Point	Treatment group	Subjects in population			95% Confidence Interval	P-value
			N	n	%		
FAS 	Right and left midface combined at Month 6	Restylane Volyme					
		Control					
		Difference					
PP 	Right and left midface combined at Month 6	Restylane Volyme					
		Control					
		Difference					

1) Subjects with a missing MMVS score have their values imputed using BOCF up to Month 6.

2) No imputation is used for PP analysis. Only subjects with complete data are included.

Note: Responder is defined as a subject with an improvement of at least one grade on the MMVS from baseline.

Note: Responder rate (%) =  $n/N \times 100$

CCI

 GALDERMA	<small>Title</small> SAP, 43CH1626, Restylane Volyme Midface	<small>Doc id</small> MA-35135
--	--	--

[figure not shown]
CCI

Effective date: 2017-11-03 11:43

*Effective*

Version: 1.0

 GALDERMA	<small>Title</small> SAP, 43CH1626, Restylane Volyme Midface	<small>Doc id</small> MA-35135
---	--	--

[figure not shown]

 GALDERMA	<small>Title</small> SAP, 43CH1626, Restylane Volyme Midface	<small>Doc id</small> MA-35135
--	--	--

CCI

 GALDERMA	<small>Title</small> SAP, 43CH1626, Restylane Volyme Midface	<small>Doc id</small> MA-35135
--	--	--

CCI

[figure not shown]
[figure not shown]

 GALDERMA	<small>Title</small> SAP, 43CH1626, Restylane Volyme Midface	<small>Doc id</small> MA-35135
--	--	--

Effective date: 2017-11-03 11:43

*Effective*

Version: 1.0

 GALDERMA	<small>Title</small> SAP, 43CH1626, Restylane Volyme Midface	<small>Doc id</small> MA-35135
--	--	--

[figure not shown]
Effective date: 2017-11-03 11:43

Effective date:

CCI

CCI

*Effective*

Version: 1.0

[figure not shown]
 GALDERMA	<small>Title</small> SAP, 43CH1626, Restylane Volyme Midface	<small>Doc id</small> MA-35135
--	--	--

Effective date: 2017-11-03 11:43

*Effective*

Version: 1.0

CCI

*Effective*

Effective date: 2017-11-03 11:43

Version: 1.0

 GALDERMA	<small>Title</small> SAP, 43CH1626, Restylane Volyme Midface	<small>Doc id</small> MA-35135

CCI
		

 GALDERMA	<small>Title</small> SAP, 43CH1626, Restylane Volyme Midface	<small>Doc id</small> MA-35135
---	--	--

[figure not shown]
Effective date: 2017-11-03 11:43

Effective date:

*Effective*

Version: 1.0

CCI

[figure not shown]

Effective date: 2017-11-03 11:43

*Effective*

Version: 1.0

 GALDERMA	<small>Title</small> SAP, 43CH1626, Restylane Volyme Midface	<small>Doc id</small> MA-35135
--	--	--

[figure not shown]

*Effective*

Effective date: 2017-11-03 11:43

Version: 1.0

 GALDERMA	<small>Title</small> SAP, 43CH1626, Restylane Volyme Midface	<small>Doc id</small> MA-35135
--	--	--

 GALDERMA	<small>Title</small> SAP, 43CH1626, Restylane Volyme Midface	<small>Doc id</small> MA-35135
--	--	--

Effective date: 2017-11-03 11:43

*Effective*

Version: 1.0

[figure not shown]
CCI

Effective date: 2017-11-03 11:43

*Effective*

Version: 1.0

 GALDERMA	<small>Title</small> SAP, 43CH1626, Restylane Volyme Midface	<small>Doc id</small> MA-35135
--	--	--

[figure not shown]

 GALDERMA	<small>Title</small> SAP, 43CH1626, Restylane Volyme Midface	<small>Doc id</small> MA-35135
--	--	--

Effective date: 2017-11-03 11:43

*Effective*

Version: 1.0

[figure not shown]

Effective date: 2017-11-03 11:43

*Effective*

Version: 1.0

 GALDERMA	<small>Title</small> SAP, 43CH1626, Restylane Volyme Midface	<small>Doc id</small> MA-35135
---	--	--

[figure not shown]
 GALDERMA	<small>Title</small> SAP, 43CH1626, Restylane Volyme Midface	<small>Doc id</small> MA-35135
--	--	--

Effective date: 2017-11-03 11:43

*Effective*

Version: 1.0

[figure not shown]
CCI

Effective date: 2017-11-03 11:43

*Effective*

Version: 1.0

 GALDERMA	<small>Title</small> SAP, 43CH1626, Restylane Volyme Midface	<small>Doc id</small> MA-35135

CCI
 		

[figure not shown]
 GALDERMA	<small>Title</small> SAP, 43CH1626, Restylane Volyme Midface	<small>Doc id</small> MA-35135
---	--	--

Effective date: 2017-11-03 11:43

*Effective*

Version: 1.0

CCI

[figure not shown]
 GALDERMA	<small>Title</small> SAP, 43CH1626, Restylane Volyme Midface	<small>Doc id</small> MA-35135
--	--	--

Effective date: 2017-11-03 11:43

*Effective*

Version: 1.0

CCI

 GALDERMA	<small>Title</small> SAP, 43CH1626, Restylane Volyme Midface	<small>Doc id</small> MA-35135
---	--	--

2017-11-03 11:43

Effective date:

*Effective*

Version: 1.0

## 10 Appendix A7: Safety evaluation

CCI

 GALDERMA	<small>Title</small> SAP, 43CH1626, Restylane Volyme Midface	<small>Doc id</small> MA-35135
--	--	--

Effective date: 2017-11-03 11:43

*Effective*

Version: 1.0

[figure not shown]
CCI

Effective date: 2017-11-03 11:43

*Effective*

Version: 1.0

 GALDERMA	<small>Title</small> SAP, 43CH1626, Restylane Volyme Midface	<small>Doc id</small> MA-35135
--	--	--

 GALDERMA	Title SAP, 43CH1626, Restylane Volyme Midface	Doc id MA-35135
--	---	---------------------------

## 10.2 Adverse Events

### 10.2.1 Summary of Adverse Events (AEs)

**Table 10-5: Brief summary of all AEs, Safety population**

	Group A N = xx		Group B					
			No treatment at baseline N = xx		Treatment with Restylane Volyme N = xxx		Subjects	
	n	%	n	n	%	n	n	%
Any AEs reported, total								
AEs related to product and/or injection procedure								
Of which were serious								
AEs unrelated to product and/or injection procedure								
of which were serious								
Subjects with no AE reported								

% = n/N\*100

Note: Treatment with Restylane Volyme columns include data from subjects in the Restylane Volyme group after their initial treatment at baseline, as well as data from subjects in the Control group after their initial treatment at Month 6.

 GALDERMA	Title SAP, 43CH1626, Restylane Volyme Midface	Doc id MA-35135
---	---	---------------------------

### 10.2.2 Related AEs

**Table 10-6: Related AEs occurring throughout the whole study period by MedDRA System Organ Class, Preferred Term, and maximum intensity, Safety population, Group B**

Primary System Organ Class Preferred Term	Maximum intensity	No treatment at baseline N = xx		Treatment with Restylane Volyme N = xxx		Total N = xx	
		Subjects	Events	Subjects	Events	Subjects	Events
		n (%)	n	n (%)	n	n (%)	n
Any related AE	Total						
	Mild						
	Moderate						
	Severe						
SOC1	Total						
	Mild						
	Moderate						
	Severe						
PT11	Total						
	Mild						
	Moderate						
	Severe						
PT12	Total						
	Mild						
	Moderate						
	Severe						
SOC2	Total						
	Mild						
	Moderate						
	Severe						
PT21	Total						
	Mild						
	Moderate						
	Severe						

% = n/N\*100

Note: Treatment with Restylane Volyme columns include data from subjects in the Restylane Volyme group after their initial treatment at baseline, as well as data from subjects in the Control group after their initial treatment at Month 6.

 GALDERMA	Title SAP, 43CH1626, Restylane Volyme Midface	Doc id MA-35135
---	---	---------------------------

**Table 10-7: Duration (number of days days) of related AEs occurred throughout the whole study period by MedDRA System Organ Class and Preferred Term, Safety population, Group B**

Primary System Organ Class Preferred Term	No treatment at baseline N = xx					Treatment with Restylane Volyme N = xxx					Total N = xxx				
	N (events)	Duration missing	Mean (SD)	Median	Min-Max	N (events)	Duration missing	Mean (SD)	Median	Min-Max	N (events)	Duration missing	Mean (SD)	Median	Min-Max
SOC1															
PT11															
PT12															
Total															

Note: Treatment with Restylane Volyme columns include data from subjects in the Restylane Volyme group after their initial treatment at baseline, as well as data from subjects in the Control group after their initial treatment at Month 6.

**Table 10-8: Time to onset (days) since most recent treatment of related AEs by MedDRA System Organ Class and Preferred Term, Safety population, Group B**

Primary System Organ Class Preferred Term	No treatment at baseline N = xx				Treatment with Restylane Volyme N = xxx				Total N = xxx			
	N (events)	Mean (SD)	Median	Min-Max	N (events)	Mean (SD)	Median	Min-Max	N (events)	Mean (SD)	Median	Min-Max
SOC1												
PT11												
PT12												
Total												

Note: Treatment with Restylane Volyme columns include data from subjects in the Restylane Volyme group after their initial treatment at baseline, as well as data from subjects in the Control group after their initial treatment at Month 6.

 GALDERMA	Title SAP, 43CH1626, Restylane Volyme Midface	Doc id MA-35135
---	---	---------------------------

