
Signed Agreement of the Clinical Study Protocol

CTN:

43CH1626

Title of the CSP:

A randomized, multi-center, evaluator-blinded, no-treatment controlled study to evaluate the effectiveness and safety of Restylane Volyme for correction of Midface Volume Deficit and/or Midface Contour Deficiency

I, the undersigned, have read and understand the protocol specified above, and agree on the contents. The study protocol, the Clinical Trial Agreement and the additional information given in the Investigator Brochure for Restylane Volyme will serve as a basis for co-operation in this study.

Principal Investigator

Printed name

Signature

Date

Study site

Version: 1.0

	Title 43CH1626 Clinical Study Protocol	Doc id MA-33281
--	--	---------------------------

2016-12-09 17:18

Effective date:

Effective

Version: 1.0

Synopsis

Title of study:	A randomized, multi-center, evaluator-blinded, no-treatment controlled study to evaluate the effectiveness and safety of Restylane Volyme for correction of Midface Volume Deficit and/or Midface Contour Deficiency
Clinical Trial Number:	43CH1626
Countries involved, number of sites/country, number of subjects:	The study will be conducted at approximately 5 sites in China. Group A: Up to 20 subjects (2 first treated subjects per Treating Investigator, each site will have 2 treating investigators as maximum) will be enrolled as group A. These subjects will all receive treatment with Restylane Volyme. Group B: Evaluator treatment-blind group with approximately 148 subjects will be randomized in a CC1 ratio to treatment group or no-treatment control group, i.e., 111 subjects assigned to the Treatment Group and 37 subjects assigned to the Control Group.
Objectives:	
 • To evaluate the effectiveness of Restylane Volyme in the treatment of Midface Volume Deficit and/or Midface Contour Deficiency • To evaluate the safety of Restylane Volyme in the treatment of Midface Volume Deficit and/or Midface Contour Deficiency
Endpoints:	Primary effectiveness endpoint: 
 • Percentage of responders, defined by at least 1 point improvement from baseline on the MMVS on both sides of the face concurrently, as measured by the blinded evaluator at 6 months after last treatment in Treatment Group, and at 6 months after randomization in Control Group. 
CC1

[figure not shown]
[figure not shown]
Effective date: 2016-12-09 17:18

Effective

Version: 1.0

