4.2 Number of Subjects

The study will be performed at approximately 5 sites in China and approximately 168 subjects will be enrolled.

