4.8.1.2 Baseline (D1)

- Weight
- Medical history/concurrent diseases
- Vital signs (pulse rate, blood pressure, respiratory rate, axillary temperature)
- Inclusion and exclusion criteria
- Pregnancy test for childbearing potential women
- Photography (before injection)
- Randomization
- MMVS (by Blinded Evaluator and **CCI** [REDACTED])
- Treatment
- **CCI** [REDACTED]
- Concomitant medications /procedures
- Device deficiencies
- AE since last visit

4.8.1.3 Optional Touch-up 4W ($\pm 3d$) after randomization (only for subjects who receive touch-up)

- Weight
- Photography (before injection)
- **CCI** [REDACTED]
- [REDACTED]
- Pregnancy test for childbearing potential women (before injection)
- Treatment
- **CCI** [REDACTED]
- [REDACTED]
- Concomitant medications/procedures

	
Title 43CH1626 Clinical Study Protocol
	
Doc id MA-33281

--	--	-----------------------------------

2016-12-09 17:18

Effective date:

Effective

Version: 1.0

- Device deficiencies
- AE since last visit

4.8.1.4 4W ($\pm 3d$) after last treatment

- Weight
- Photography
- Note: extra set of photos (taken 10 minutes after the first photos) will be taken and used for validation as needed.
- CCI
- [REDACTED]
- Concomitant medications /procedures
- AE since last visit

4.8.1.5 3M ($\pm 1w$), 6M ($\pm 1w$) and 9M ($\pm 2w$) Follow-up after last treatment

- Weight
- Photography
- MMVS (by Blinded Evaluator and CCI [REDACTED])
- CCI [REDACTED]
- Concomitant medications /procedures
- AE since last visit
- Laboratory tests (Only performed at 6M)

4.8.1.6 12M ($\pm 2w$) after last treatment Final visit or Early termination

- Weight
- Photography
- MMVS (by Blinded Evaluator and CCI [REDACTED])
- CCI [REDACTED]
- Pregnancy test for childbearing potential women
- Concomitant medications/procedures
- AE since last visit
- Laboratory tests (Only performed at early termination if termination occurs before 6 months visit after last treatment)
- Study termination

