- Pregnancy test for childbearing potential women (before injection)
- Treatment
- CCI [REDACTED]
- [REDACTED]
- Concomitant medications /procedures
- Device deficiencies
- AE since last visit

4.8.2.7 4W ($\pm 3d$) Follow-up after last treatment

- Weight
- Photography
- CCI [REDACTED]
- [REDACTED]
- [REDACTED]
- Concomitant medications /procedures
- AE since last visit

4.8.2.8 3M ($\pm 1w$) Follow-up after last treatment

- Weight
- Photography
- MMVS (by Blinded Evaluator and CCI [REDACTED])
- CCI [REDACTED]
- [REDACTED]
- Concomitant medications /procedures
- AE since last visit

4.8.2.9 6M ($\pm 1w$) after last treatment Final visit / early termination

- Weight
- Photography

	
Title 43CH1626 Clinical Study Protocol
	
Doc id MA-33281

--	---	-----------------------------------

2016-12-09 17:18

Effective date:

Effective

Version: 1.0

- MMVS (by Blinded Evaluator and **CCI** [REDACTED])
- **CCI** [REDACTED]
- [REDACTED]
- Pregnancy test for childbearing potential women
- laboratory tests (haematology and serum chemistry)
- Concomitant medications /procedures
- AE since last visit
- Study termination

5 Subjects

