### 2.5.2 Adverse Events

All AEs will be coded according to MedDRA and summarized by System Organ Class (SOC) and Preferred Term (PT). All AE summaries defined below will be presented by treatment, i.e. no treatment at baseline vs. all treated subjects (at baseline and Month 6).

An overall summary of number and percentage of subjects with any AEs, including related/unrelated and serious AEs, and the number of events will be compiled (Table 10-5).

For related AEs, maximum intensity of the AE will be summarized (Table 10-6). The duration (Table 10-7) and time to onset (Table 10-8) of event will be summarized by SOC and PT using number of events, mean, standard deviation, minimum, median, and maximum statistics. Action taken due to a related AE will be summarized by SOC, and PT (Table 10-9) using number of events.

Number and percentage of subjects with unrelated AEs and number of events will be presented by SOC, PT and maximum intensity (Table 10-10).

Time to onset of an AE will be derived as the start date minus the date of the most recent treatment. If the start date is missing, it will be assumed that the AE started on the date of the most recent treatment.

Duration of an AE will be derived as the stop date minus the start date +1. If the start date is missing, it will be assumed that the AE started on the date of the most recent treatment. Missing stop date will not be imputed and therefore no duration will be calculated in these cases. Instead, the number of AEs that were ongoing at the end of the study will be given.

 GALDERMA	<small>Title</small> SAP, 43CH1626, Restylane Volyme Midface	<small>Doc id</small> MA-35135
---	--	--

[figure not shown]

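### The treated adverse-event column pools 12-month and 6-month follow-up after injection, so late-onset events are diluted by up to 25% in relative terms

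*SAP*

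**What the plan says.** SAP 2.5.2 presents all adverse-event summaries as two columns: subjects untreated at baseline, and everyone treated, whether at baseline or at Month 6. The notes to Tables 10-5 to 10-10 define the second column as the Restylane Volyme group after initial treatment at baseline, "as well as data from subjects in the Control group after their initial treatment at Month 6".

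Tables 10-5, 10-6 and 10-10 give percentages as n/N × 100 with a single N for that column. Table 10-6 covers related events over the whole study. Table 10-8 gives the number of events and the mean, SD, median and range of days from the most recent treatment to onset. It has no percentage of subjects.

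The two groups in the column have different schedules. The last visit in SAP Table 4-5 (Restylane Volyme arm) is "12M after last treatment". In SAP Table 4-6 (control) it is "6M after last treatment". Protocol 4.8.1.6 and 4.8.2.9 agree. Protocol 8.4.4 runs adverse-event reporting to the last scheduled visit.

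The Group B sizes in the protocol synopsis are "111 subjects assigned to the Treatment Group and 37 subjects assigned to the Control Group". Treatment at Month 6 is offered to controls, not required (protocol 4.1).

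**The concern.** A crude percentage assumes that everyone in the denominator could have been seen to have the event. That holds for reactions in the first days after injection. It fails for an event that starts 8 months after the last injection: the Restylane Volyme arm is still attending visits, while the crossed-over controls have left the study but remain in N.

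Incidence and onset of adverse events are stated safety endpoints (protocol 3.2.3, SAP 1.6). The gel stays in place for several months (protocol 2.2), and the 9- and 12-month visits are the only scheduled source of information on late reactions. Diluting that information lowers the apparent late-event rate, in the product's favour. A reader of Table 10-6 cannot detect or undo this, because its rows are not split by time of onset.

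The issue lies inside the treated column. It would remain even if treated and untreated subjects were compared correctly over the first 6 months.

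**Working it through.** **Inputs**
- Restylane Volyme arm 111, control 37 (protocol synopsis).
- Scheduled follow-up after last treatment: 12 months for the arm, 6 months for treated controls (protocol 4.8.1.6 and 4.8.2.9; SAP Tables 4-5 and 4-6).
- Control uptake at Month 6: not stated; assumed 50% to 100%.
- Withdrawals: not stated in the readable text; ignored at first.

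**Reproducing the plan's own figures**
- Group B: 111 + 37 = 148, as stated.
- Total: 5 sites × 2 investigators × 2 subjects = 20 in Group A, and 148 + 20 = 168, as stated.
- Duration, arm: 21 days screening + 28 days to touch-up + 12 months = 13.6 months.
- Duration, control: 21 days + 6 months + 28 days + 6 months = 13.6 months.

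Both durations match the stated 14 months or so. Total duration is therefore equal in the two groups, and the difference appears only when follow-up is counted from the injection.

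**Follow-up behind the pooled column (full uptake)**
- Total: 111 × 12 + 37 × 6 = 1,554 person-months, a mean of 1,554/148 = 10.5 months.
- Beyond month 6: 111 × 6 = 666 person-months, all from the Restylane Volyme arm.

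**Dilution of late-onset events**

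With control uptake u, N = 111 + 37u. If x subjects have a late event, the pooled percentage is x/N and the percentage among those scheduled for observation is x/111. The ratio is 111/N.

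| Uptake u | N | 111/N | Relative understatement |
|---|---|---|---|
| 100% | 148 | 0.750 | 25% |
| 90% | 144.3 | 0.769 | 23% |
| 80% | 140.6 | 0.789 | 21% |
| 50% | 129.5 | 0.857 | 14% |

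If all 4 subjects in a preferred-term row had only late events, the row would read 4/148 = 2.7%, against 4/111 = 3.6%.

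**Effect on a mixed row**

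Let e be the proportion with an early event, equal in both groups, and l the proportion of the arm with a late event only. The arm's row is e + l and the pooled row is e + l × 111/N. The gap is l × (1 − 111/N). If 2 of those 4 subjects already had an early event in the row, only the other 2 matter. The gap is then 2/111 − 2/148 = 1.80% − 1.35% = 0.45 percentage points, whatever the size of e.

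**Table 10-8**

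With a early and b late events per treated arm subject, and the same early rate in controls, the late share of events is b/(a + b) in the arm. In the pooled column at full uptake it is 0.75b/(a + 0.75b). Late onsets are under-represented, so the mean moves earlier. If most onsets fall on the day of treatment, the median may not move. The maximum still shows the latest onset.

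**The case against.** The strongest reply is that pooling suits the events that matter most in number. Protocol 8.4.8 says typical reactions start on the day of treatment and resolve within a week. Both groups are fully observed for these, pooling uses every exposed subject, and the choice is disclosed in SAP 2.5.2 and the table notes. Crude n/N is a common descriptive convention. This stands for early events and for rows that they dominate.

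Four stronger readings are tempting, and the documents do not support them:
- A reader might infer that every treated-column percentage is 25% too low. Only subjects whose sole event in a row starts after month 6 are diluted, and no readable table isolates late onset.
- A reader might infer that Table 10-8 has the wrong denominator. It counts events and has no subject denominator.
- A reader might infer that late related events in controls cannot be captured at all. Protocol 8.4.6 requires related events that start after participation ends to be reported to the sponsor. That route is a paper form without scheduled visits, and no use in these tables is stated, so ascertainment is weaker but not nil.
- A reader might infer that an upper confidence limit for late events would be misreported. SAP 2.5 plans descriptive safety summaries, and the readable text plans no such limit.

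SAP 2.1, part of SAP 2.5 and the start of protocol 10.5 are redacted, so a rule on time windows or subgroups there cannot be excluded. The readable table shells and notes show none.

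**Conclusion.** The concern holds for late-onset events. One column with one N combines subjects scheduled for 12 and for 6 months after last injection. In the percentage tables, the contribution of related events starting after month 6 is understated by 25% in relative terms at full control uptake, 21% at 80% and 14% at 50%. In rows that also hold early events the shift is small, 0.45 percentage points in the example above. In Table 10-8 the effect is mixed censoring at about 6 and 12 months, which mainly affects the mean.

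These sizes assume the planned 111 and 37, no withdrawals, and no use of the post-study reports in the tables. Losses from the Restylane Volyme arm before the late window would widen the gap: at an assumed 10% loss, 99.9/148 = 0.675 of the column would be under observation. The primary endpoint is not affected. This is a cheap improvement to the reporting of a stated safety endpoint.

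**What to change.** In Tables 10-5, 10-6 and 10-10, and in Table 10-8, do one of the following:
- show the treated column also by randomised group: the Restylane Volyme arm, and controls after Month 6 treatment; or
- limit the pooled column to onset within 6 months after last injection.

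In either case, report related events with later onset in a separate row, with the number still under observation (at most 111) as denominator. Table 10-5 must change together with Table 10-6, or the headline summary and the detailed table will rest on different bases.

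The cost is extra columns or rows in the adverse-event table shells. No new data are needed, since onset dates, treatment dates and randomised group are already recorded.
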